4.0 Study Endpoints (if applicable)

Aim 1: Pre and post-test data collection, storage, and scoring calculations will be carried on by study coordinator/PhD student.

Pediatric Evaluation of Disability Computerized Adaptive Test (PEDI CAT) using a study iPad: The PEDI CAT measures 0 to 18-year-old children's abilities across three domains of mobility, selfcare and social function. It can be used with all pediatric diagnosis, across settings, and measures change following an intervention. It demonstrates excellent reliability⁴⁸, good validity^{49,50} with a minimal detectable change ranging between 2.2 to 3.3 across domains.⁵¹ Our study will measure only selfcare and mobility domains, which takes approximately 20 minutes to administer. Scaled (criteria referenced) and Standard (normative referenced) PEDI-CAT scores will be calculated.

6-Minute Walk Test (6MWT)

The 6MWT has demonstrated good reliability and validity in various pediatric populations.^{52,53} It has also been found to be predictive of cardiovascular fitness in survivors of children with pediatric cancers.⁵⁴ The 6MWT takes 6 minutes to administer.

Aim 2: Daily data collection by art and physical therapists during or after sessions, but data will be managed by study coordinator/PhD student following the sessions.

The Self-Assessment Manikin (SAM): The SAM is an image-based tool used to evaluate affective change in pleasure, arousal, and dominance in response to an object or event.⁵⁵⁻⁵⁷ (Appendix 6) Good reliability and validity of the SAM has been demonstrated.⁵⁸ Suggestions are that it perform similarly across diverse cultures and ages.⁵⁹⁻⁶¹ The SAM has been collected in studies involving exercise in which large

effect sizes were noted.⁶² We plan to use the computerized application of the SAM, which will take seconds to administer before and after daily AT and PT interventions.

Respiratory Sinus Arrhythmia derived from Heart Rate Variability: HRV measures short-term R-to-R intervals, which is reflective of the autonomic nervous system. The portable, non-invasive Firstbeat Bodyguard 2 (Appendix 7) will be worn to gather HRV. The monitor will be placed on the chest of the child 10 minutes prior to the beginning of AT and worn by the child until removal following PT. We will evaluate the first and last 5-minute of HRV data during the AT session. Using Cardio Batch software, RSA will be calculated from the HRV data. The Firstbeat Bodyguard 2 accurately measures 99.95% of the heartbeats compared to standard EKG.⁶³ Placement and removal of the HRV monitor requires only seconds. The study coordinator/PhD student will clean all HRV files for artifact and calculate RSA values using Cardio Batch software. At the end of each day, the coordinator/PhD student will be responsible for collecting, cleaning, scoring, and storing all daily data.

Aim 3: Daily collection: Daily data collection by art and physical therapists during or after sessions, but data will be managed by study coordinator/PhD following the sessions.

Walking distance during PT session as measured by accelerometer: The ActiGraph GT9X Link (Appendix 8) will collect walking distance as measures by distance and steps during PT. It is similar in looks and wear to an iWatch. It has demonstrated good reliability and validity.^{64,65} It can collect a variety of outcomes (e.g., energy expenditure, body position, sleep), but for aim 3, we will be most interested in walking distance and number of steps. At the end of each day, the study coordinator/PhD student will be responsible for collecting, calculating distance and step values using Actigraphy software, and storing accelerometry data.

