3.0 Intervention to be studied (if applicable)

Side-by-side integration of AT and PT has not been examined and we propose to conduct a clinical trial in which for two weeks daily (Monday-Friday), 20 children between the ages of 3-18 years will be randomly assigned into one of two groups: 1) collaborative intervention: 45 minutes of AT immediately followed by 30 minutes of PT or 2) PT only intervention: 30 minutes. During the collaborative intervention of week 1, oil pastels will be the media and week 2 gouache painting without brush.

Treatment: 45 minutes of AT closely followed by 30 minutes of PT OR 30 minutes of PT.

AT treatments will seek to reduce sympathetic dominance/physiological and emotional distress. Oil pastels will be used for Days 1-5 and gouache painting for days 6-10. Art therapy is a collaborative, interactive, and iterative process that evolves across the session between the child and art therapist, as such, outside of the actual change in medium, there is no study specific art therapy prescription or protocol. Art therapy sessions will occur in the child's room.

PT treatments will seek to prevent physical deconditioning and encourage mobility, ambulation, and selfcare participation based on participant's ability. Physical therapy sessions will occur in the child's room and on the HCT unit.

The same art and physical therapist and art therapist will conduct children's session across the 2-week study duration. This art and physical therapist commonly work on the HCT unit. The coordinator again will monitor all sessions to ensure the following of study procedures.

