10.0 Study Design / Methods

Design: Randomized clinical trial to compare collaborative AT and PT to only PT in children undergoing HCT.

Using excel, the study coordinator will randomize each participant to either the PT and AT or PT only group. Each group will be assigned 10 participants.

Power

With a recruitment expectation of 30 participants, we expect a 30% drop out rate leaving 20 enrolled participants and feel confident that this study's aim 2 and 3 will be successfully powered to identify statistical significance ($p<0.05$) in outcomes. For Aims 2 and 3 which involve the collection of clustered data for HRV, SAM, and walking distance, in order to identify a medium effect, 80% or 90% power will be achieved with 61 or 82 measurement points respectively.^{54,55,66,67} Accounting for a dropout rate of 30%, the expected number of participants is 20. With 10 participants in the intervention group, 100 measurement points for HRV, SAM, and walking distance each are expected; thus, ensuring adequate power for aim 2 and 3.

For the PEDI CAT and 6MWT, to achieve 80% power, the projected sample size in each group is estimated to be 16 and 20; therefore, we proposed that we may not be adequately powered for aim 1.^{51,68} However, findings attributed to aim 1 will provide pilot data to inform a larger randomized control trial. Although aim 1 may not be adequately powered, the published minimal detectable change (MDC) for the PEDI CAT selfcare and mobility domains are 2.2 and 2.5 respectively while the Minimally Clinically Important Difference (MCID) for the 6MWT is 7%.^{69,70} Although, power to find a statistically significant difference may be inadequate, we expect to observe this level/magnitude of improvement in our proposed study. Variation values from this aim will provide data that are essential to guide future research.

Data Analyses

Aim 1: In children undergoing HCT during in-patient care, do a randomized group receiving a combination of Physical Therapy (PT) plus Art Therapy (AT) have improved functional activity level outcomes of self care and mobility as measured by the Pediatric Evaluation of Disability Inventory Computerized Adaptive Test and the 6-Minute Walk Test, compared with a group receiving PT only.

Hypothesis 1: Children receiving the combined intervention of PT plus AT will demonstrate greater improvements in self care and mobility skills.

Statistical Test: Independent sample t-tests

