Aim 2: Do children receiving PT plus AT have physiological (sympathetic or parasympathetic) and emotional responses to oil pastels and gouache as measured by respiratory sinus arrhythmia derived from heart rate variability and Self-Assessment Manikin scores during each of the daily AT sessions.

Hypothesis 2: Oil pastels or gouache AT will generate a RSA value in the direction of needed parasympathetic activity and balance the emotions of valence, arousal, and dominance.

Statistical Test: Repeated measures generalized linear regression

Aim 3: In children receiving PT plus AT, determine if there is a stronger association between the RSA values of oil pastels or gouache AT and an increased walking distance as measured by accelerometry during daily PT sessions.

Hypothesis 3: The media that best generates a parasympathetic RSA value and emotional balance will be associated with a greater walking distance.

Statistical Test: Repeated measures generalized linear regression

Data Collection

The 10-day intervention will begin on approximately Day 15 of HCT. Pre-test (Pediatric Evaluation of Disability Inventory and 6-Minute Walk Test) will be collected on Day 14. The same post-test data will be collected the day following the tenth day of intervention.

During the 10 days of intervention, the Self Assessment Manikin, heart rate variability, and walking distance will be collected daily.

The study coordinator will be responsible for storing all data. All documentation and data concerning each participant will be coded to protect confidentiality. All data collection and storage processes and locations will use study equipment (i.e., heart rate variability monitors, computers, College of Health Professions DA server) that is password protected, encrypted, and behind the MUSC firewall. All study related equipment will be locked in the office of the PI when not in use. There will be no transfer of data to a third party.

Procedures

- 1) IRB approval
- 2) Begin participant enrollment
- 3) Collaborate with HCT team to initiate recruitment and share study flyer
- 4) PI will obtain informed consent from participants in the hospital or electronically through MUSC secure email.
- 5) Randomize participant to AT and PT or PT only
- 6) Approximately Day 14 of HCT complete pre-test (Pediatric Evaluation of Disabilities Inventory and 6-Minute Walk Test)

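### The coordinator role allocates, monitors sessions, runs and scores the Aim 1 tests and cleans the HRV files, with no masking planned; coding the HRV files before cleaning is a cheap way to reduce the risk of bias

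*Combined protocol and SAP*

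**What the plan says.** Four duties fall to the coordinator role.

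- **Allocation** (section 10.0): "Using excel, the study coordinator will randomize each participant to either the PT and AT or PT only group".
- **Session oversight** (section 3.0): "The coordinator again will monitor all sessions to ensure the following of study procedures".
- **Aim 1 outcomes**, the PEDI CAT and the 6MWT (section 4.0): "Pre and post-test data collection, storage, and scoring calculations will be carried on by study coordinator/PhD student".
- **HRV processing** (section 4.0, Aim 2): "The study coordinator/PhD student will clean all HRV files for artifact and calculate RSA values using Cardio Batch software". The timing is the end of each day, when "the coordinator/PhD student will be responsible for collecting, cleaning, scoring, and storing all daily data".

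Two further facts matter. In the section 10.0 procedures, step 5 is "Randomize participant to AT and PT or PT only" and step 6 is "Approximately Day 14 of HCT complete pre-test", so allocation comes before baseline testing. In section 3.0 the medium follows the calendar: "Oil pastels will be used for Days 1-5 and gouache painting for days 6-10".

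The plan does not mention masking of the assessor, the HRV cleaner or the analyst. It gives no artifact rule and does not say how the walk test is to be conducted. Sections 3.0 and 10.0 refer to the coordinator; section 4.0 joins coordinator and PhD student with a slash, which could mean one person or two.

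**The concern.** Treatment is necessarily open to the child, the family and the therapists. In such a trial, the main protection left for a performance test is an assessor who does not know the arm. Here the role that assigns the arm and sees the sessions also runs and scores the tests, before and after treatment. An error at either time point enters the comparison of improvement.

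This matters more because of how Aim 1 will be read. Section 10.0 concedes that Aim 1 may be underpowered. It turns instead to magnitude (2.2 and 2.5 points on the PEDI CAT domains, 7% on the 6MWT) and offers the results as pilot data for a larger trial. Assessor expectation distorts point estimates, a larger sample does not average it away, and the next trial would be planned on the distorted values.

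For RSA the comparison is between media within the PT plus AT arm. Knowledge of the day is therefore the issue, not knowledge of the arm. Someone who has monitored the session and cleans its recording that evening knows which medium was used. Without a rule, decisions about what counts as artifact are open to that knowledge.

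**Working it through.** The plan gives no figure for bias or masking, so there is nothing to reproduce. The check sets the duties side by side, then gives an illustration of scale and the cost of the remedy.

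**1. What the measurer can know at each step**

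| Measurement | Done by | Knowledge available |
|---|---|---|
| Pre-test (step 6) | coordinator/PhD student | arm, since allocation is step 5 |
| Post-test (step 8) | coordinator/PhD student | arm, from allocation and from monitoring sessions |
| HRV cleaning (end of day) | coordinator/PhD student | day, hence medium; also first or last 5-minute segment |

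If the slash means two people, the second could in principle be unaware of allocation, but nothing in the plan keeps that person unaware.

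**2. Scale for Aim 1 (illustration; the shift is an assumption)**

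Inputs: 10 per arm and independent-samples t-tests (section 10.0). The 0.05 level is stated there for Aims 2 and 3 and is assumed here for Aim 1, two-sided. The true effect is set to zero. Let b be the net between-arm shift due to the assessor, in SD units of the analysed score.

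The t statistic is then noncentral t with df = 2 × 10 − 2 = 18 and noncentrality b × √(10/2) = 2.236b. For b = 0.3 the noncentrality is 0.671.

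| Assumed b (SD) | Falsely favours PT plus AT | Any rejection, two-sided |
|---|---|---|
| 0 | 2.5% | 5.0% |
| 0.1 | 4.0% | 5.5% |
| 0.2 | 6.2% | 7.1% |
| 0.3 | 9.3% | 9.7% |
| 0.5 | 18.4% | 18.5% |

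The table shows what a given shift would do. It is not evidence that any shift will occur.

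**3. Direction**

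Hypothesis 1 favours PT plus AT, so an assessor's expectation in Aim 1 would have a natural direction. Hypothesis 2 says oil pastels or gouache, without choosing between them, so no direction follows for RSA.

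**4. Cost of the remedy**

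- Testing time: section 4.0 gives about 20 minutes for the two PEDI CAT domains and 6 minutes for the 6MWT, 26 minutes in all. For 20 children, 26 × 20 = 520 minutes, or 8.7 hours per time point. Two time points take 1,040 minutes, or 17.3 hours. This is administration time only.
- HRV segments: 10 children × 10 sessions × 2 segments (first and last 5 minutes of AT) = 200 segments to code if every session is completed.

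**The case against.** Several counter-arguments have force.

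- **The instruments limit the bias.** The PEDI CAT is a computerised adaptive test, RSA is calculated by software, and section 4.0 cites 99.95% heartbeat accuracy for the monitor against EKG. This stands as a limit. It does not cover the conduct of the walk test, and it does not exclude artifact in moving children; the plan itself expects to clean every file.
- **A reader might infer that one person edits the recordings by hand.** The documents do not say so. They do not say whether cleaning is manual or automatic, and the slash leaves the number of people open. What is supported is cleaning by an unmasked role with no stated rule.
- **A reader might infer that unmasked cleaning pushes RSA towards the hypothesis.** It cannot, because the hypothesis prefers neither medium. The background reports an earlier adult study favouring oil pastels, but the plan does not adopt that as its prediction.
- **A reader might infer that the present team could eliminate the problem.** The documents name nobody who is trained, free and unaware of the arm. The therapists deliver treatment and the co-investigators' study duties are not described. The PI takes consent, receives event reports from the therapists and reviews collected outcome data monthly with the co-investigators. Children and parents know the arm, and the PEDI CAT respondent is not stated, so respondent bias could remain.
- **Aim 1 is only pilot work.** This lowers the stakes for inference, but not for the estimates handed to the next trial.

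**Conclusion.** The point holds as an avoidable weakness in how outcomes are measured and processed. As written, the plan leaves the Aim 1 pre- and post-tests open to an assessor who knows the arm, and RSA processing open to a cleaner who knows the medium.

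The size of any bias cannot be derived from the documents. The 0.1 to 0.5 SD range is assumed and serves only to show how a 10-per-arm t-test responds. For RSA, neither size nor direction can be claimed.

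The conclusion rests on reading the slash as one role with shared knowledge. If two people hold it and one is deliberately kept unaware of allocation, the Aim 1 part weakens, but the plan would have to say so. Masking the cleaner also leaves untouched the confounding of medium with week that comes from the fixed order of media.

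**What to change.** 1. **HRV files (section 4.0, Aim 2).** Replace end-of-day cleaning with batch cleaning. Before cleaning, an existing team member other than the cleaner gives each segment a random code that hides day, medium and whether it is the first or last segment. Clean under one artifact rule written in advance, and unmask only after the RSA values are locked. The cost is later cleaning and a little recoding time for up to 200 segments. This is the clearest gain and needs no new staff.
2. **6MWT.** Write one fixed script with set encouragement phrases and use it for every child at both tests. The cost is close to nil.
3. **Aim 1 assessor.** Where an existing team member does not attend sessions and can be kept unaware of the arm, have that person give both the pre-test and the post-test, so that the assessor does not change between time points. This takes about 17 hours of administration for 20 children, plus scheduling and any training. If that person takes part in the monthly data review, what they see there must not reveal the arm. If nobody qualifies, state in the report that Aim 1 assessors were unmasked.

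Sample size and treatment are unchanged.

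### The treating therapists collect the children's SAM ratings of their own sessions with no stated safeguard, which mainly exposes the before-to-after SAM change in Aim 2

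*Combined protocol and SAP*

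**What the plan says.** Section 4.0 opens its Aim 2 part with "Aim 2: Daily data collection by art and physical therapists during or after sessions", and continues "but data will be managed by study coordinator/PhD student following the sessions". The SAM falls under that heading: "We plan to use the computerized application of the SAM, which will take seconds to administer before and after daily AT and PT interventions". Later in the same section, at the end of each day, "the coordinator/PhD student will be responsible for collecting, cleaning, scoring, and storing all daily data". Coming at day's end, this reads as retrieving and processing data already recorded, not as giving the SAM to the child.

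Section 3.0 adds three relevant facts:
- One team treats throughout: "The same art and physical therapist and art therapist will conduct children's session across the 2-week study duration".
- The order of media is fixed for every child in the PT plus AT arm: "Oil pastels will be used for Days 1-5 and gouache painting for days 6-10".
- A third person oversees the work: "The coordinator again will monitor all sessions to ensure the following of study procedures".

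For Aim 1, Section 4.0 gives pre- and post-test collection to the coordinator, so the plan already separates therapist from assessor there.

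The documents do not say who hands the device to the child, whether the therapist watches or sees the answers, or what is said to the child.

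**The concern.** The SAM is the plan's emotional outcome, and it is a self-rating by a child. Section 5.0 admits children from age 4 (Section 3.0 says 3), and the youngest may need an adult to prompt them. As written, the adult who collects the rating has just delivered the session being rated. A child may rate the after-session state more favourably to please that adult, and the adult's expectations may colour the prompting. Either would appear as a before-to-after gain that the session did not cause.

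The media contrast is at risk in a narrower way. The Background reports that gouache without a brush provokes high engagement and anxiety, and that pastels did better than gouache in an earlier adult study. Study staff may therefore expect different things of the two media. With pastels always first, growing familiarity with the therapist would also fall on gouache.

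Two further uses depend on the SAM. Hypothesis 3 refers to the medium that best produces emotional balance, and Section 13.0 lists the SAM among the data reviewed monthly for signs of harm. Ratings raised to please could affect both.

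**Working it through.** **Planning figure.** The plan gives no size for rating bias, so there is no figure to reproduce on this point. The only planning figure that covers the SAM is in Section 10.0: 61 or 82 measurement points for 80% or 90% power at a medium effect. With an assumed d of 0.5 and a two-sided 0.05 test of two independent groups, 61 and 82 per group give 78.9% and 89.3%, close to the stated values. Changing who gives the SAM alters none of this.

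**Inputs from the documents.** 10 children in the PT plus AT arm; 5 sessions per medium and 10 in all; significance at 0.05.

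**Assumptions.** The SD of one session's before-to-after change is 1. The test is two-sided, a paired or one-sample t-test on child means with 9 degrees of freedom (critical value 2.262). The planned method is repeated measures generalized linear regression, so the t-test is only an illustration. There is no true effect. τ² denotes the child-by-medium variance in A and the between-child variance in B.

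**A. Pastel-gouache contrast.** If the shift is the same under both media, the bias in the difference is 0 and the false-positive rate stays at 5%. If it differs by b, then SE = √[2(τ² + 1/5)/10] and the noncentrality is b/SE.

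| τ² | SE | b = 0.2 | b = 0.3 | b = 0.5 |
|---|---|---|---|---|
| 0 | √0.04 = 0.200 | 14.6% | 26.9% | 60.6% |
| 0.1 | √0.06 = 0.245 | 11.3% | 19.5% | 44.6% |
| 0.3 | √0.10 = 0.316 | 8.8% | 13.6% | 29.3% |

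The ranges are therefore 9-15%, 14-27% and 29-61%. The upper ends need the child-by-medium variance to be zero.

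**B. Before-to-after change over 10 sessions.** A shift c in the after rating does not cancel. SE = √[(τ² + 1/10)/10].

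| τ² | SE | c = 0.2 | c = 0.3 |
|---|---|---|---|
| 0.1 | √0.02 = 0.141 | 24.5% | 47.4% |
| 0.3 | √0.04 = 0.200 | 14.6% | 26.9% |

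That is 15-25% for 0.2 SD and 27-47% for 0.3 SD.

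**Choice of unit.** If the SD of 1 belongs to each single rating and the errors are independent, a change score has variance 2. In A, the term 1/5 then becomes 2/5. At τ² = 0 the rates for b = 0.3 and 0.5 are 16% and 35%; at τ² = 0.3 they are 11% and 22%. The direction is unchanged and the size is smaller.

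**Number of ratings.** Before and after AT and before and after PT is 4 a day. 10 children × 10 days × 4 = 400 ratings at most in the PT plus AT arm.

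**The case against.** The strongest objection is that Aim 2 compares media within the same children, treated by the same therapists. Who collects the rating does not change between media, so a constant wish to please cancels. This stands. A reader might infer that any pastel-gouache gap simply reflects who is asking. The documents do not support that: Hypothesis 2 names no favoured medium, and nothing shows that therapist expectations actually differ by medium. The Background makes a difference possible, and the fixed order would mix any drift with medium, but both remain conditional. The before-to-after change has no such protection.

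Second, RSA is an Aim 2 outcome recorded by a device in the same sessions. A reader might infer that Aim 2 has nothing to set against the SAM. That is too strong, because RSA is not open to a child's wish to please when rating. It does not, however, measure what the child reports feeling.

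Third, the SAM is computerized, and collection by therapists may mean no more than passing over a tablet. This is fair: the therapist's presence or prompting at the moment of rating is not stated. But collection is assigned to the therapists, and computer entry alone does not ensure privacy or neutral wording.

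Fourth, the coordinator is not blinded, since Section 10.0 has the same person randomize the children, and the child knows the medium. A reader might infer that using the coordinator would remove the bias. It would not; it could reduce it.

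**Conclusion.** The point holds as a modest design weakness with a cheap improvement. Section 4.0 assigns the child's self-rating to the therapists whose sessions are rated and states no protection. The before-to-after SAM change is the result mainly exposed; the media contrast is exposed only if the effect varies by medium or over time.

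The size is unknown. The calculated rates show how sensitive a 10-child comparison would be to assumed shifts, and are not estimates of bias in this trial. A reader might take the largest media figures, 27% and 61%, as the expected inflation. They are only the tops of the ranges for 0.3 and 0.5 SD, and they rest on zero child-by-medium variance.

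**What to change.** In Section 4.0, state that the coordinator hands the tablet to the child before and after each session and reads one fixed neutral script, the same for both media. The child enters the SAM privately, with the therapist out of view and unable to see the answers.

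This takes a sentence or two in the protocol and a short script. The downside is about a minute of coordinator time per rating. For up to about 400 ratings that is about 400 minutes (400/60 = 6.7 hours) in the PT plus AT arm, or 4 minutes per child per day. Section 3.0 says that the coordinator monitors all sessions but not that they are at the bedside at each rating, so their presence at those moments should be confirmed.

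The change does not separate medium from week. That confounding comes from the fixed order and remains whoever collects the SAM.

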PROTOCOL TITLE: The effect of a collaborative art therapy and physical therapy intervention on children undergoing a hematopoietic cell transplant: a randomized clinical trial

PRINCIPAL INVESTIGATOR: [name], PT, PhD, PCS

Objectives / Specific Aims

Aim 1: In children undergoing HCT during in-patient care, does a randomized group receiving a combination of PT plus AT have improved functional activity level outcomes of selfcare and mobility as measured by the Pediatric Evaluation of Disability Inventory Computerized Adaptive Test (PEDI CAT) and the 6-Minute Walk Test (6MWT), compared with a group receiving PT only.

Hypothesis 1: Children receiving the combined intervention of PT plus AT will demonstrate greater improvements in selfcare and mobility skills.

Aim 2: Do children receiving PT plus AT have different physiological (sympathetic or parasympathetic) and emotional responses to oil pastels and gouache as measured by respiratory sinus arrhythmia (RSA) derived from heart rate variability (HRV) and Self-Assessment Manikin (SAM) scores during each of the daily AT sessions.

Hypothesis 2: Oil pastels or gouache AT will generate a greater RSA value in the direction of needed parasympathetic activity and balance in the emotions of valence, arousal, and dominance.

Aim 3: In children receiving PT plus AT, determine if there is a stronger association between the RSA values of oil pastels or gouache AT and an increased walking distance as measured by accelerometry during daily PT sessions.

Hypothesis 3: The media that best generates a parasympathetic RSA value and emotional balance will be associated with a greater walking distance.

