- 7) Day 15-24 of HCT: 45 minutes of AT and 30 minutes of PT OR 30 minutes of PT only. Heart rate variability, Self Assessment Manikin, accelerometry collected across sessions.
- 8) Approximately Day 25 of HCT complete post-test (Pediatric Evaluation of Disabilities Inventory and 6-Minute Walk Test)
- 9) Data analyses and dissemination.

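### Aim 2 does not say which SAM rating is analysed and makes no use of the before-AT rating that the trial already plans to collect

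*Combined protocol and SAP*

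**What the plan says.** SAM timing is described in several places.

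- **Objectives, Aim 2:** "Self-Assessment Manikin (SAM) scores during each of the daily AT sessions". The Data Analyses part of section 10.0 repeats this almost unchanged.
- **Section 4.0, opening line for Aim 2:** "Daily data collection by art and physical therapists during or after sessions".
- **Section 4.0, SAM paragraph:** "which will take seconds to administer before and after daily AT and PT interventions". The same paragraph presents SAM as a measure of affective change in response to an object or event.
- **Section 10.0, Power:** "100 measurement points for HRV, SAM, and walking distance each are expected".
- **Section 10.0, Data Collection and Procedures:** "the Self Assessment Manikin, heart rate variability, and walking distance will be collected daily", and "Heart rate variability, Self Assessment Manikin, accelerometry collected across sessions". Neither gives a time point.

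For the Aim 2 analysis, section 10.0 names a type of regression and nothing more. It does not state the SAM response variable, a baseline term or the ratings to be included. For HRV, section 4.0 specifies the opening and closing five minutes of the AT session. SAM has no equivalent statement.

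**The concern.** Aim 2 asks whether children respond differently, physiologically and emotionally, to oil pastels and gouache. SAM is its only emotional measure. The collection schedule yields a rating before each AT session and another after it, but the analysis text does not say what becomes of them. An analyst could take the after-AT score, the change across AT, or the after-AT score adjusted for the before-AT score, and each would be a fair reading of the plan.

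Two things are at stake. First, the choice would be made with the data in hand, separately for valence, arousal and dominance. Second, the simplest reading, an unadjusted score per session, discards information. Children in transplant care arrive at a session in a mood shaped by that day's symptoms and procedures. That day-to-day variation goes into the error term unless the before-AT rating is used to remove it.

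**Working it through.** **1. The plan's own count.** The intervention group has 10 children ("With 10 participants in the intervention group") with 10 sessions each. One point per session gives 10 × 10 × 1 = 100, which is the stated figure. The SAM paragraph implies 4 raw ratings per day, or 3 if the after-AT rating also serves as the before-PT rating. That is 400 or 300 ratings. The 100 therefore fits one summary per session, but the documents do not say which summary.

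**2. Inputs for the comparison of definitions.**
- From the documents: 10 children; 5 oil pastel and 5 gouache sessions per child (section 3.0); alpha 0.05. Sidedness is not stated and is taken as two-sided.
- Assumed, because the documents give no SAM variance, correlation or numeric effect: session-level SD 1 within a child; true medium effect 0.6 on the after-AT rating; no effect of that session's medium on the before-AT rating; same-day correlation ρ between the two ratings of 0.3, 0.5 or 0.7; the same medium effect in every child.

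**3. Formula.** Each child contributes one gouache-minus-pastel difference of means, analysed by a t-test on 9 df (critical value 2.262). For the after-AT rating alone:
- Variance of one child's difference = 1/5 + 1/5 = 0.4.
- Standard error over 10 children = √(0.4/10) = 0.2.
- Noncentrality = 0.6/0.2 = 3.0.

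The other definitions keep the effect at 0.6 and multiply the error variance by a factor: 2(1 − ρ) for the before-to-after change, and 1 − ρ² for the after-AT rating adjusted for before-AT. Noncentrality is 3.0 divided by the square root of that factor.

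**4. Results.**

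| SAM definition | ρ = 0.3 | ρ = 0.5 | ρ = 0.7 |
|---|---|---|---|
| After-AT only: factor / noncentrality / power | 1 / 3.00 / 76% | 1 / 3.00 / 76% | 1 / 3.00 / 76% |
| Change: factor / noncentrality / power | 1.40 / 2.54 / 62% | 1.00 / 3.00 / 76% | 0.60 / 3.87 / 93% |
| After-AT adjusted for before-AT: factor / noncentrality / power | 0.91 / 3.15 / 80% | 0.75 / 3.46 / 87% | 0.51 / 4.20 / 96% |

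The adjusted row treats the slope on the before-AT rating as known. Estimating it from the same data (5,000 simulated trials per setting) gives 79%, 86% and 96%, so the ordering does not change.

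**5. Reading.** Adjustment is at least as good as either alternative at every correlation tried. A change score is worse than ignoring the baseline when ρ is below 0.5 and better when it is above. Adjustment does not require knowing ρ in advance.

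**The case against.** The strongest reply is that the sections do not really conflict, and most of it stands.

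- **The aim text points to AT ratings.** It ties Aim 2 to the AT sessions, and the SAM paragraph is a collection schedule. A reader might infer that all daily ratings, including those around PT, will be pooled and the media contrast diluted. No section proposes that. With the same assumed 0.6 SD effect, pooling four ratings would give an estimate of 0.15 with no carry-over into PT (power 12% to 17%). With full carry-over it would give 0.45, with power of about 83%, 72% and 62% at ρ = 0.3, 0.5 and 0.7. The last case is closest to the trial's premise that AT benefit carries into PT, and at ρ = 0.3 it exceeds the 76% for after-AT alone. These figures illustrate a possible misreading, not the plan.
- **A baseline rating is planned.** A reader might infer from the opening line of Aim 2 in section 4.0 that no pre-session rating is taken. That line says mainly who collects and manages the data, and it recurs for Aim 3. It also covers HRV, whose monitor goes on ten minutes before AT. The only instruction specific to SAM includes a rating beforehand.
- **The count of 100 is not a contradiction.** HRV has two windows per session and is also counted as 100.
- **A change score is defensible**, since the protocol describes SAM as measuring affective change.
- **Adjustment has a cost in meaning.** From the second session with a medium onward, the before-AT rating follows earlier use of that medium. Any effect that builds up over days is partly absorbed, so the adjusted contrast describes the within-session response.

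The reply does not supply the missing definition. The documents name neither the SAM response nor the handling of baseline.

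**Conclusion.** The point holds as a gap in definition and an inexpensive gain in efficiency. The SAM outcome for Aim 2 is unspecified, and a planned same-session baseline has no stated use. Under the assumptions above, using it raises power from 76% to about 80%, 87% or 96% for correlations of 0.3, 0.5 and 0.7. The gain is small at the low end and substantial at the high end. Its true size cannot be known from the documents.

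The documents do not support the stronger claims that the media comparison will be diluted, that its baseline will be lost, or that the sections give irreconcilable schedules. The fixed order of the two media is a separate matter, which this change does not address.

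**What to change.** In the Aim 2 part of Data Analyses (section 10.0), define the SAM outcome for each dimension (valence, arousal, dominance) as the after-AT rating, one per session, with the same session's before-AT rating as a covariate in the repeated-measures model. Add that ratings around PT do not enter the media comparison; they can be reported descriptively. State that the adjusted contrast estimates the within-session response to the medium.

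Then carry the definition through: the Aim 2 wording in the Objectives, the opening Aim 2 line in section 4.0 (so that it allows for ratings before as well as after sessions), and the Power text, where the 100 SAM points should be described as one after-AT rating per session.

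The cost is a few sentences and one covariate. The ratings are already scheduled, so there is no new data collection and no added burden on the children. The definition should be fixed before any SAM data are analysed.
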